7.6 Expedited Adverse Event Reporting to Overall PI

Investigators **must** report to the Overall PI any serious adverse event (SAE) that occurs following the subject’s written consent, during treatment, or within 100 days of the last dose of treatment on the local institutional SAE form.

In the event of an unanticipated problem or life-threatening complications, treating investigators must immediately notify the overall PI.

Investigators will report AEs directly to the DFCI Office for Human Research Studies (OHRS) per the DFCI IRB reporting policy, using the local institutional SAE form.

7.7 DF/HCC Expedited Reporting Guidelines

Investigative sites within DF/HCC will report AEs directly to the DFCI Office for Human Research Studies (OHRS) per the DFCI IRB reporting policy.

Other investigative sites will report AEs to their respective IRB according to the local IRB's policies and procedures in reporting adverse events. A copy of the submitted institutional AE form should be forwarded to the Overall PI within the timeframes detailed in the table below.

Attribution	DF/HCC Reportable AEs				
	Gr. 2 & 3 AE Expected	Gr. 2 & 3 AE Unexpected	Gr. 4 AE Expected	Gr. 4 AE Unexpected	Gr. 5 AE Expected or Unexpected
Unrelated Unlikely	Not required	Not required	5 calendar days [#]	5 calendar days	24 hours [*]
Possible Probable Definite	Not required	5 calendar days	5 calendar days [#]	5 calendar days	24 hours [*]
[#] If listed in protocol as expected and not requiring expedited reporting, event does not need to be reported.					
[*] For participants enrolled and actively participating in the study or for AEs occurring within 30 days of the last intervention, the AE should be reported within 1 business day of learning of the event.					

The Overall PI will submit AE reports from outside institutions to the DFCI OHRS according to DFCI IRB policies and procedures in reporting adverse events.

7.8 Expedited Adverse Event Reporting to the Food and Drug Administration (FDA)

The Overall PI, as study sponsor, will be responsible for all communications with the FDA. The Overall PI will report to the FDA, regardless of the site of occurrence, any serious adverse event that meets the FDA's criteria below for expedited reporting:

Report any unexpected fatal or life-threatening suspected adverse reactions no later than 7 calendar days after initial receipt of the information. Submit 7-day reports by a rapid means of communication (preferably fax). Each submission should be address to the Regulatory Project Manager and/or to the Chief, Project Management Staff.

SAEs should be reported on MedWatch Form 3500A, which can be accessed at: <http://www.accessdata.fda.gov/scripts/medwatch/>. Send the SAE forms as follows:

By [contact]

OR

By mail:
MEDWATCH
[name]
[name]
Fax: [name] ([name])
<http://www.accessdata.fda.gov/scripts/medwatch/>

7.9 Expedited Adverse Event Reporting to Hospital Risk Management

Participating investigators will report to their local Risk Management office any participant safety reports or sentinel events that require reporting according to institutional policy.

7.10 Expedited Adverse Event Reporting to BMS

SAEs, whether related or not related to study drug, and pregnancies must be reported to BMS within 24 hours. SAEs must be recorded on BMS or an approved form; pregnancies on a Pregnancy Surveillance Form.

SAE Email Address: [contact]

SAE [contact]

If only limited information is initially available, follow-up reports are required. (Note: Follow-up SAE reports should include the same investigator term(s) initially reported.)

If an ongoing SAE changes in its intensity or relationship to study drug or if new information becomes available, a follow-up SAE report should be sent within 24 hours to the BMS (or designee) using the same procedure used for transmitting the initial SAE report.

7.11 Multi-Center Trial Specifications

For Multi-Center Trials where a DF/HCC investigator is serving as the Sponsor, each participating institution **must** abide by the reporting requirements set by the DF/HCC. This applies to any medical event equivalent to an unexpected grade 2 or 3 with a possible, probable or definite attribution, unexpected grade 4 toxicities, and grade 5 (death) regardless of study phase or attribution.

8. PHARMACEUTICAL INFORMATION

A list of the adverse events and potential risks associated with the investigational agents administered in this study can be found in section 7.3.

Product information table: please also see respective product investigator brochures

Table Product Description					
Product Description and Dosage Form	Potency	Primary Packaging (Volume)/ Label Type	Secondary Packaging (Qty) /Label Type	Appearance	Storage Conditions (per label)
Nivolumab (BMS-936558-01) Solution for Injection	100 mg (10 mg/mL)	10 mL vial	5 vials per carton/ Open-label	Clear to opalescent colorless to pale yellow liquid. May contain particles	2 to 8°C. Protect from light and freezing
Lirilumab (BMS-986015-01) Solution for Injection	100 mg (10 mg/mL)	10 mL vial	5 vials per carton/Open-label	Clear to opalescent, colorless liquid. Essentially free of particles	2 to 8°C. Protect from light and freezing

8.1 Storage and Stability

If stored in a glass front refrigerator, vials should be stored in the carton. Recommended safety measures for preparation and handling of nivolumab and lirilumab include laboratory coats and gloves.

For additional details on prepared drug storage and use time of nivolumab or lirilumab under room temperature/light and refrigeration, please refer to section 5 of this protocol.

8.2 Handling

Qualified personnel, familiar with procedures that minimize undue exposure to themselves and the environment, should undertake the preparation, handling, and safe disposal of the chemotherapeutic agent in a self-contained and protective environment.

8.3 Availability

Free of cost, investigational supply of nivolumab and lirilumab, will be provided by Bristol-Myers Squibb.

8.4 Ordering

Dana-Farber Research Pharmacy will request supply of nivolumab and lirilumab from Bristol-Myers Squibb, by submitting an order form, provided by Bristol-Myers Squibb.

8.5 Accountability

Accountability for investigational agents at the study site is the responsibility of the sponsor-investigator. Study drug will be dispensed only to eligible patients by Dana-Farber Research Pharmacy. The appropriate study personnel will maintain records of study drug receipt and dispensing at Dana-Farber Research Pharmacy. A careful record of the inventory and disposition of the agent will be maintained, using the NCI Drug Accountability Record Form (DARF).

8.6 Destruction and Return

Unused supplies and expired supplies of the investigational agents will be destroyed on site, by the Dana-Farber Research Pharmacy, per institutional SOP.

9. BIOMARKER, CORRELATIVE, AND SPECIAL STUDIES

Correlative studies are planned as part of this study. At the time of biopsy to demonstrate recurrence, tumor tissue will be sent for multiparametric flow cytometry (Belfer Center for Applied Cancer Science, DFCI), a portion of fresh-frozen, paraffin-embedded (FFPE) tissue will be obtained for genomic sequencing and for immunohistochemistry (IHC) for immune marker staining (e.g. PD-1, PD-L1/L2) and/or multiplexed immunofluorescence (MIF). Flow cytometry, sequencing and IHC/MIF data will be gathered to characterize distinct tumor immunophenotypes and these findings will be correlated with outcomes.

9.1 Biomarker Studies

Biopsy confirmed squamous cell carcinoma of the head and neck is a requirement to be enrolled on this study. A separate, fresh research biopsy is mandatory prior to starting treatment on study if tumor is accessible, otherwise archival tissue will be accepted. At the time of definitive surgical resection, after adequate tumor for pathological assessment has been harvested as deemed appropriate by the surgeon, remaining tissue will also be obtained for research purposes. If relevant, tissue may also be obtained at the time of first recurrence after surgery for research purposes.

Tumor biopsies and/or surgery should not generally be performed on Friday afternoons, as there may not be time for processing of fresh tissue samples. If a biopsy or surgical resection is performed on Friday morning, [name] of the Belfer Center for Applied Cancer Science should be notified ahead of time to ensure that there will be adequate time for processing fresh tissue or serum samples, since these should not be stored over the weekend.

Each tumor and blood sample obtained will be assigned a unique coded identifier in order to preserve the confidentiality of the participant. The coded samples will be linkable to the participant, but the key that links that person to the unique identifier will be stored in a database housed on a server at the DFCI. Access to participant identity will be provided only to the principal investigator and study staff (not laboratory staff). There are multiple firewalls and passwords protecting the data from unwanted viewers. Patient privacy will be maintained by strictly curtailing access to the electronic file via passwords and firewalls. The coded samples

will be cryopreserved and stored in secure locked freezers. Once all research is complete, the link between the coded samples and patient identifiers will be destroyed.

At the time of blood sample collection (see *Study calendar*), 2 tubes are requested:

1. 2 tubes drawn in 8 mL whole blood, purple top tubes for circulating immune profiling
2. 2 tubes drawn in 8 mL whole blood, purple top tubes for neoantigen T cell profiling

Multiparametric flow cytometry

At the time of pre-treatment biopsy and surgical resection, two cores of fresh tissue will be allocated to two 1.5 mL centrifuge tubes (one core in each tube) in RPMI containing 10% fetal bovine serum (FBS). Additionally, at the time of pre- and post-treatment biopsy and at specified time points during and after treatment, two tubes of peripheral blood (obtained at a minimum of 3 time points during the study) will be obtained per standard collection protocols – drawn in phlebotomy or clinic and captured in 8 mL whole blood, purple top tubes. The volume of blood to be collected per blood draw for study purposes will not exceed 40 mL. All specimens will be de-identified and labeled with the participant's initials, study ID number and the date of acquisition. After collection, the tissue and blood collection tubes should be delivered immediately to the lab of [name] and [name] [office: LC-4315J, Robert and Renee Belfer Center for Applied Cancer Science, [name], [contact] or [contact]]. The specimen must arrive in a timely fashion to facilitate processing for evaluation of immune cells. Tissue will be prepared as a cell suspension that will be stained using fluorescently-conjugated antibody cocktails for human immune markers (surface antibodies include: CD45, CD3, CD4, CD8, CD69, CD38, CCR7, LAG-3, TIM-3, PD-1, CD45RA, HLA-DR, CTLA-4, CD16, CD56, CD31, CD33, PD-L1, PD-L2, GITR, CD15, CD19, and CD14). Cells will be analyzed within 72 hours of fixation on a BD Fortessa cell analyzer with FACSDiva software v8.0.1 (BD Biosciences) and gated using FlowJo software v10.

Immunohistochemistry

At the time of pre-treatment biopsy and surgical resection, one core of fresh tissue will be allocated to a standard orange-top specimen cup containing 10% neutral buffered formalin. The specimen will be labeled with the participant's initials, medical record number and the date of acquisition. After collection, the specimen will be sent to the Brigham & Women's Hospital (BWH) pathology division for processing. Following standard tissue processing, sectioning and slide preparation for histopathologic review, the specimen will be stored in accordance with BWH protocols (both tissue blocks and tissue slides). At a later time, we will then request tissue block retrieval through the Pathology Specimen Locator Core with preparation of 5 unstained slides through the Specialized Histopathology (SHP) Core service at BWH. SHP will then prepare 1 stained hematoxylin & eosin slide, 1 slide stained for PD-1, 1 slide stained for PD-L1 and 2 unstained slides will be stored for additional studies. These slides will be retrieved from the SHP in Thorn Building, 6th floor, room 603 at the BWH by the study principal investigator. In collaboration with an oral histopathologist, [name] of the BWH Department of Oral Medicine and Dentistry, the slides will be analyzed and scored based on stained immune parameters.

Genomic sequencing

At the time of pre-treatment biopsy and surgical resection, one core of fresh tissue will be allocated to 5 mL of RPMI media in a 15 mL conical tube for the purposes of DNA and RNA sequencing efforts. Once prepared, aliquoted core material for sequencing will be delivered immediately to the laboratory of [name] at the DFCI [Dana Building, 8th floor, room 819, [name], office: [contact]].

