1.3 Secondary Objectives

- To evaluate toxicity; radiologic and clinicopathologic responses
- To estimate DFS from the time of salvage surgery
- To estimate overall survival (OS) from the time of salvage surgery
- To characterize distinct tumor immunophenotypes and correlate these findings with outcomes

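### The IHC specimen label conflicts with the protocol's coded-sample rule and, separately, nothing masks the slide scorer to time point, response or outcome

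*Combined protocol and SAP*

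**What the plan says.** Section 9.1 opens with a general rule: "Each tumor and blood sample obtained will be assigned a unique coded identifier in order to preserve the confidentiality of the participant". On who may know whose sample it is, it adds: "Access to participant identity will be provided only to the principal investigator and study staff (not laboratory staff").

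The Immunohistochemistry paragraph of the same section describes a core taken at the pre-treatment biopsy and another at resection. Of each it says: "The specimen will be labeled with the participant's initials, medical record number and the date of acquisition". The specimen goes to the hospital pathology division for processing and storage. At some unspecified later date the block is recalled, sections are cut, and one slide each is stained with haematoxylin and eosin, for PD-1 and for PD-L1. The slides are collected "by the study principal investigator". Then, with an oral histopathologist collaborating, "the slides will be analyzed and scored based on stained immune parameters".

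The flow cytometry paragraph uses a different label: "All specimens will be de-identified and labeled with the participant's initials, study ID number and the date of acquisition".

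Section 1.3 lists among the secondary objectives: "To characterize distinct tumor immunophenotypes and correlate these findings with outcomes". Section 9 names IHC or multiplexed immunofluorescence, with flow cytometry and sequencing, as sources for that work. Section 13 calls the correlative studies exploratory.

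**The concern.** There are two problems, and they should be kept apart.

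The first is a contradiction. A medical record number identifies the patient directly. Sending it to a pathology laboratory does not fit a rule that codes every sample and withholds identity from laboratory staff.

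The second is a missing safeguard. Staining scores involve judgement. The trial is open label with no control arm, and the slides may be read after response, and perhaps recurrence, is known. A scorer who knows which slide is post-dose, or which patient relapsed, can drift towards the expected result. Without a control arm, that drift cannot be told apart from a drug effect. At stake are the before/after change in IHC markers and the association of immunophenotype with outcome.

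**Working it through.** **1. Labelling.**

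| Text in Section 9.1 | Identifier | Stated access |
|---|---|---|
| General rule | Unique code on each tumour and blood sample | Principal investigator and study staff; not laboratory staff |
| Flow cytometry | Initials, study ID, date | Described as de-identified |
| IHC | Initials, medical record number, date | Sent to pathology division; no recoding step described |

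Only the IHC row carries a medical record number. The rule makes no exception for it, so the statements conflict on their face.

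**2. Masking.** I looked in Sections 9, 9.1 and 13 for each element that would protect the scoring.

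- Scorer masked to patient, time point, response or outcome: not mentioned.
- Scoring method or scale: not mentioned.
- Second reader: not mentioned.
- Date of reading relative to outcome: not fixed; slides are cut later than collection.
- Label on the stained slides: not described. If the specimen's acquisition date is carried over, it separates biopsy from resection.
- Who scores besides the histopathologist: not named. Retrieval by the principal investigator is explicit; scoring by that person is not.

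**3. The plan's nearby figure.** Section 13 gives 81% power for a 0.42 SD within-patient change with n = 50, using a two-sided 0.05 Wilcoxon signed-rank test. For normal differences the test's relative efficiency is 3/π:

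- effective n = 50 × 3/π = 47.75, with square root 6.910
- noncentrality = 0.42 × 6.910 = 2.902
- power from the noncentral t distribution = 81.1%; simulation (40,000 runs) = 81.4%

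The stated figure reproduces and is not in dispute.

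**4. Illustration only.** Assume no true change and a constant scoring shift δ, in SD units, between time points. The documents give no value for δ. Approximately,

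rejection rate = Φ(6.910δ − 1.96) + Φ(−6.910δ − 1.96).

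At δ = 0.1 this is Φ(−1.269) + Φ(−2.651) = 0.102 + 0.004 = 10.6%. Simulation gives:

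| Assumed shift (SD) | False-positive rate |
|---|---|
| 0 | 5.0% |
| 0.05 | 6.1% |
| 0.1 | 10.5% |
| 0.2 | 27.0% |
| 0.3 | 52.8% |

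Three limits apply. Section 13 ties its n = 50 to cluster-differentiation markers in tumour and blood, which may not include the IHC scores. The calculation treats the score as continuous, while no IHC scale is given. And a constant before/after shift would not by itself distort a correlation of baseline score with outcome; bias from knowing the outcome is a different mechanism and is not quantified here.

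**The case against.** The strongest reply is that this is silence on masking for one exploratory assay, of a kind often left to a laboratory manual. Much of that stands. Section 13 calls the work exploratory and describes descriptive and graphical summaries, IHC is one of three sources for the immunophenotype, and no survival or safety analysis uses the scores.

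Three stronger readings are tempting, and the documents do not support them.

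- A reader might infer that the scored slides carry initials, record number and date. The text gives that label to the specimen, not to slides cut later.
- A reader might infer that the principal investigator scores the slides. Participation is plausible, since someone collaborates with the histopathologist, but only retrieval is stated.
- A reader might infer that unmasked scoring breaks the coding rule. That rule is there for confidentiality and expressly lets the principal investigator know identity. Scoring by that person would not breach it, and coding alone would not mask anyone.

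It can also be said that a pathology division ordinarily works with record numbers and that the rule does not say the code must be the only label. That may explain the IHC label, but the section states no exception.

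The reply does not dispose of the gap. Exploratory status lowers the stakes, but it does not protect a before/after comparison from a reader who knows which slide is which.

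**Conclusion.** The point holds in two limited parts. The IHC specimen label conflicts with the coded-sample rule and the passages must be reconciled. Independently, the IHC procedure, followed exactly as written, allows subjective scores to be given with time point, response and outcome known.

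Severity is low. The effect is confined to the exploratory marker comparison and the secondary immunophenotype objective; primary disease-free survival is untouched. The size of any bias cannot be derived from the documents. The error rates above rest on assumed shifts and on a sample size that may not apply to IHC. They show what unmasked scoring could do, not that it will happen. The conclusion assumes that no separate laboratory manual already provides masking; the documents cite none for this step.

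**What to change.** In the Immunohistochemistry paragraph, have the histopathology core label the stained slides with the Section 9.1 code only, without initials, record number or date, and supply them in random order. The same pathologist scores them without knowledge of time point, response or outcome, and scores are locked before the code is linked to patient data. State who else, if anyone, takes part in scoring, and apply the same masking to them. In the same edit, reconcile the specimen label with the coding rule, either by using the code or by stating an explicit exception for the pathology division.

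The cost is small. If the slide list applies to each specimen, 3 stained slides × 2 time points = 6 relabelled slides per patient, or at most 6 × 58 = 348 over all registered patients. No additional reader or patient procedure is needed. Random order and score locking do require some batching and a person who holds the code. Treatment-related tissue changes may partly reveal the time point, so masking may be incomplete.

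Label: cheap improvement, low severity.

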9.2 Multi-center Guidelines

Non-DF/HCC sites will be responsible for shipping samples to Dana-Farber on the day of collection. Specific shipping instructions will be provided separately.

10. STUDY CALENDAR

Screening evaluations are to be conducted within 3 weeks prior to study registration. Procedures done within a week of study registration don't need to be repeated to establish baseline. Scans and x-rays must be done ≤ 4 weeks prior to the start of therapy. Laboratory evaluations do not need to be repeated to meet eligibility criteria on cycle 1 day 1, if they were done within 3 days of the first treatment dose. In an event that the participant's condition is deteriorating, laboratory evaluations should be repeated within 48 hours prior to initiation of the next cycle of therapy. Each treatment cycle in this study is 28 days long.

Assessments must be performed prior to administration of any study agent. Study assessments and agents should be administered within ± 3 days of the protocol-specified date, unless otherwise noted.

	Screening	Window Phase	Pre-surgery	Surgery	Adjuvant phase							End of Treatment	Follow up visit 30 days after last dose
					Cycle 1		Cycle 2		Cycle 3		Cycle 4-6		
					Day 1	Day 15	Day 1	Day 15	Day 1	Day 15	Day 1		
Informed consent	X												
Medical History	X												
Concomitant Medicines	X												
Physical exam (Ht, Wt, VS, PS) ^a	X	X			X	X	X	X	X	X	X	X	X
Routine labs ^b	X	X			X	X	X	X	X	X	X	X	X
FSH (if female <55 years old)	X												
HPV testing (oropharyngeal only)	X												
B-HCG (WOCBP only) ^c	X									X	X		
ECG	X									X	X		

Radiologic evaluation ^{d, g}	X		X	X								
Biopsy sample ^{e, f}	X										X ^h	
Correlative biopsy ^f	X										X ^h	
Correlative blood ⁱ	X ⁱ					X					X	
Nivolumab		X		X	X	X	X	X	X	X		
Lirilumab		X		X		X		X		X		
Adverse event evaluation		X		X	X	X	X	X	X	X	X	X

- a) Physical exam is symptom directed. Height measured at screening only.
- b) Routine labs include: CBC, LFTs, CMP, Mg, TSH, Free T4. Baseline HCV antibody, hepatitis B surface antigen, hepatitis B surface antibody, and hepatitis B core antibody testing is required. TSH and free T4 are required less frequently according to the following schedule: screening, window phase (D1 of pre-surgery immunotherapy dosing), D1 of each adjuvant cycle, and at the 30-day post protocol treatment visit.
- c) Serum or urine within 24 hours prior to first dose.
- d) PET-CT or contrast-enhanced CT imaging of the chest, abdomen and pelvis will be obtained at baseline to rule out distant disease. Contrast-enhanced neck CT or MRI at the time of screening or registration and will be repeated 1-4 days prior to salvage surgery. Interval scans (contrast-enhanced neck CT or MRI) will be performed every 8 weeks following salvage surgery or as clinically indicated while on treatment. Follow-up imaging will be performed at the end of treatment (see footnote g).
- e) Archival tissue is acceptable. Some of this tissue will also be used for correlative study.
- f) Fresh biopsy is mandatory if tumor is accessible. Fresh tissue is also collected at the time of surgery. Biopsy will also be obtained at the time of progression or recurrence, if safe to perform.
- g) Participants, regardless if they receive the adjuvant therapy, will be followed for response (at the end of the window phase of the trial) until first disease progression or recurrence and for survival throughout the trial for a total of 5 years from time of salvage surgery (or from study registration if no salvage surgery was performed). Post-end of protocol treatment, if first disease progression or recurrence has not been confirmed, tumor assessments (contrast-enhanced neck CT or MRI and PET-CT) are to continue every 3 months (+/- 1 month) until first disease progression or recurrence, death, or 2 years post-date of salvage surgery (or from study registration if no salvage surgery was performed), then every 6 months until 5 years post-date of salvage surgery (or from study registration if no salvage surgery was performed). After first disease progression or recurrence has been confirmed, patients will be followed for survival by phone only, every 3 months (+/- 1 month) until death or 5 years post-date of salvage surgery (or from study registration if no salvage surgery was performed), whichever occurs first.
- h) Recommended in the setting of disease recurrence or progression only.
- i) Screening correlative blood collection may occur at screening or at pre-surgery. Pre-surgery correlative blood collection may occur any time from the day following neoadjuvant drug administration until surgery. EOT blood draw may occur after the EOT visit.

